### **5.1. MRI Protection Mode**

Prior to an MRI scan, the pulse generator (PG) must be programmed to the MRI Protection Mode using the Programmer / Recorder / Monitor (PRM).

Pacing mode options include asynchronous pacing (DOO, AOO, VOO) or no pacing (Off).

Asynchronous pacing should only be used if the subject is pacing-independent. If MRI Protection Brady Mode is programmed to Off, the subject will not receive therapy until MRI Protection Mode is exited. Off should only be used if the subject is judged to be clinically capable of receiving no pacing during the time the pulse generator is in MRI Protection Mode, including during the scan.

Considerations prior to choosing asynchronous pacing include:

- Determine whether the patient is pacing-dependent.
- Determine which chamber(s) need to be paced.
- Consider the possibility of arrhythmia induction with asynchronous pacing.
- Subjects with the following conditions may have increased risk of developing transient pacing-dependence:
  1. At risk for intermittent AV block (for example, those with progressive AV block, or a history of unexplained syncope)
  2. At risk for trifascicular block (alternating bundle branch block or PR interval > 200 ms with LBBB or other bifascicular block)

In the MRI Protection Mode, the following features and functions are suspended:

- Bradycardia sensing
- Tachycardia detection and therapy
- PaceSafe™ automatic threshold(s)
- Daily diagnostics (Lead Impedance, Intrinsic Amplitude, Pace Threshold)
- Motion and respiratory sensors
- Magnet detection
- RF telemetry
- Battery voltage monitoring
- Beeper is disabled

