**Original Release: May 11, 2017**

**Current Version: Mar 1, 2018**

## Revision History

Revision Number	Release Date	Template number and version	Section	Change	Reason for Change
AA	May 11, 2017	90702637 Rev./Ver. AH	N/A	N/A	Initial release
AB	Jul 24, 2017	90702637 Rev./Ver. AH	Whole document	Delete requirement for magnet and LV lead delivery system, and related description and assessment.	Regulatory requirement.
AB	Jul 24, 2017	90702637 Rev./Ver. AH	Whole document	Delete non-Gore coating leads.	Regulatory requirement.
AB	Jul 24, 2017	90702637 Rev./Ver.	Whole document	Delete the assessment of Beeper function.	Regulatory and trial

Revision Number	Release Date	Template number and version	Section	Change	Reason for Change
		AH			management requests.
AB	Jul 24, 2017	90702637 Rev./Ver. AH	Table 12-3	Parameters for RV shock impedance tests added.	Protocol refinement
AC	Mar 1, 2018	90702637 Rev./Ver. AI	Contact Information	author information deleted	Based on protocol template
AC	Mar 1, 2018	90702637 Rev./Ver. AI	5.1, 6.1, 10.3, 12, 20.3	Descriptions regarding no pacing function during MRI protection mode deleted, and description on synchronization pacing added. Item 4 and 5 from exclusion criteria dropped. Requirement for 12 lead ECG and 10s ECG episode cancelled. Sections for subject evaluation before MRI and MRI visit updated.	The function of pacing under MRI protection mode was added for the device.
AC	Mar 1, 2018	90702637 Rev./Ver. AI	12.7.1.1	Lift the requirement for magnet origin.	Based on magnet availability in hospitals
AC	Mar 1, 2018	90702637 Rev./Ver. AI	12.1, 12.4	Add: A pregnancy test must be performed within 7 days prior to the index procedure in women of child-bearing potential	Trial management request

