### 12.12. Medically Necessary MRI Visits

During the study, if a subject needs a medically necessary MR scan, BSC recommends the subject be directed to have the scan at the Study site.

Note: In case the medically necessary MR scan is performed at a non-investigational site, all efforts must be made to collect the data and adhere to the MRI Conditions of Use.

Study flow is identical to the MRI visit as described in section 12.7. Some data collection is optional for Medically Necessary MRI visit as shown in italic in Table 12-11.

For medically necessary MRI scans, all activities performed by the site Principal Investigator or a sub-investigator at the MRI visit (i.e. heart rhythm monitoring) can be performed by a trained and qualified Health Care Professional (HCP).

As for the MRI visit, it is recommended to have a programmer powered ON in Zone II near the MRI room in case the patient develops the urgent need for pacing.

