## **20.3. Risks Associated with Participation in the Clinical Study**

Subjects in the MR ICD Study will have the added risk of an MR scan. Potential adverse events associated with an MR scan are minimized by assuring that the subject meets the MRI Conditions of Use. MRI scanning of patients when the Conditions of Use are met could result in the following potential adverse events, as included in the *BSC MRI Tech Guide*:

- Arrhythmia induction
- Bradycardia
- Patient death
- Patient discomfort due to slight movement or heating of the device
- Side effects of pacing at a fixed high rate such as competition with intrinsic rhythms and arrhythmias. Competitive pacing may increase the rate of pacing induced

arrhythmia until the device is reprogrammed.

- Syncope
- Worsening heart failure

MRI scanning of patients when the Conditions of Use are NOT met could result in the following potential adverse events, as included in the *BSC MRI Technical Guide*:

- Arrhythmia induction
- Bradycardia
- Damage to the pulse generator and/or leads
- Erratic pulse generator behavior
- Inappropriate pacing, inhibition of pacing, failure to pace
- Increased rate of lead dislodgement (within six weeks of implant or revision of system)
- Irregular or intermittent capture or pacing
- Loss of defibrillation therapy
- Pacing threshold changes
- Patient death
- Patient discomfort due to movement or heating of the device
- Physical movement of pulse generator and/or leads
- Sensing changes
- Syncope
- Worsening heart failure

\*\*Note: It is important to note that the risks listed in this section may lead to the subject requiring a partial or full pacing system replacement.

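### Protocol 5.1 limits asynchronous pacing to pacing-independent subjects, so a pacing-dependent subject has no permitted pacing mode during the scan

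*Combined protocol and SAP*

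**What the plan says.** Protocol 5.1 lists asynchronous pacing (DOO, AOO, VOO) and no pacing (Off) as the options while the generator is in MRI Protection Mode. Each carries a condition:

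- Asynchronous: "Asynchronous pacing should only be used if the subject is pacing-independent".
- Off: "Off should only be used if the subject is judged to be clinically capable of receiving no pacing" for as long as the mode is on.

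The considerations to be weighed before choosing asynchronous pacing follow directly. One is "Determine whether the patient is pacing-dependent". Another is to establish which chambers require pacing. A third is "Consider the possibility of arrhythmia induction with asynchronous pacing". The last begins "Subjects with the following conditions may have increased risk of developing transient pacing-dependence" and names intermittent AV block and trifascicular block. The section then lists the functions suspended in this mode, among them bradycardia sensing and tachycardia detection and therapy.

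At the MRI Visit, 12.7.3.1 requires that an appropriate pacing mode be set but gives no rule for choosing it.

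**The concern.** The condition on asynchronous pacing seems to point the wrong way. Pacing that ignores the heart's own rhythm is reserved for subjects who have a dependable rhythm, and is withheld from those who rely on the device. With Off also closed to them, pacing-dependent subjects have nowhere to go.

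This is a safety instruction for a step that every scanned subject passes through. A site with a pacing-dependent subject would have to raise a query, not scan, or depart from the text. Protocol section 16 allows departures only to protect a subject in an emergency. No statistical quantity is at stake.

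**Working it through.** There is no figure to reproduce, so the check sets the passages side by side.

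**Step 1. Could a pacing-dependent subject reach the scan?** None of the 11 exclusion criteria in 10.3 mentions pacing dependence. The nearest, item 4, concerns going without tachycardia therapy. The nearest cardiology Condition of Use in 6.1, item 5, likewise concerns tachycardia protection. Such a subject is therefore eligible and scannable as far as the protocol goes.

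**Step 2. Which modes does each kind of subject have?** Section 5.1 implies three groups. The table assumes that a pacing-dependent subject would not be judged able to go without pacing.

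| Subject | 5.1 as written | If independent is simply changed to dependent | Wording proposed under the fix |
|---|---|---|---|
| Pacing-dependent | 0 of 2 | 1 of 2 (asynchronous) | 1 of 2 (asynchronous) |
| Not dependent now, at risk of transient dependence, judged unable to go without pacing | 1 of 2 (asynchronous) | 0 of 2 | 1 of 2 (asynchronous) |
| Independent, able to go without pacing | 2 of 2 | 1 of 2 (Off) | 1 of 2 (Off) |

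The first row of the second column is the problem. The second row of the third column shows why a one-word swap is not enough: it moves the gap to a group that 5.1 itself describes.

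**Step 3. Is the sentence wrong, or is the omission deliberate?** Three things suggest that it is wrong:

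- Asking which chambers require pacing makes most sense if asynchronous pacing serves subjects who need it.
- With bradycardia sensing suspended, asynchronous pacing runs regardless of intrinsic rhythm. Section 20.3 lists "Side effects of pacing at a fixed high rate such as competition with intrinsic rhythms and arrhythmias" among the hazards of scanning. As written, 5.1 directs the mode to the subjects most exposed to that competition, while no antitachycardia therapy is available.
- The Revision History gives the reason for the change to 5.1 as "The function of pacing under MRI protection mode was added for the device". Limiting the new function to subjects who do not depend on pacing would defeat much of its purpose. The log is used here only for the stated reason, not as a discrepancy.

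Section 12.12, which also refers to the MRI visit, wants a programmer on nearby "in case the patient develops the urgent need for pacing". A need for pacing around the scan is therefore foreseen.

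If the sponsor had meant to keep pacing-dependent subjects out of the scanner, an exclusion or a Condition of Use would be expected, and neither exists.

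**Step 4. How many subjects?** At least 8 ICD + 8 CRT-D = 16 subjects must complete all sequences (13.3). Planned enrolment is 20 and may be expanded. These figures count subjects who pass through the step, not subjects affected. The documents give no figure for pacing dependence.

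**The case against.** The strongest reply is that the governing rule may lie elsewhere. Sections 5.1 and 12.7.3.1 both send the reader to the MRI Technical Guide, and section 6 requires the Conditions of Use in the protocol and in the Guide to be met. The Guide may state the rule correctly. This stands as a reason to check it first. It does not remove the problem: section 6 says that the protocol extends the Guide where they differ, which does not make the Guide prevail over 5.1.

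The evidence for inversion is also not conclusive. Determining dependence is needed under either wording. The note on transient dependence could fit the literal text, with asynchronous pacing as cover for a subject who is independent now but may lose rhythm. The risk in 20.3 concerns fixed high-rate pacing and does not itself say who should receive it. A reader might infer that the documents prove a one-word slip. They do not; they make an error likely and leave the intended rule open.

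Finally, the wording is advisory and sits in a device description, while the operative step leaves the mode to judgement. A rhythm check (12.7.2.2), a programmer kept on nearby (12.7.3.1), and continuous ECG with an external defibrillator and trained staff (12.7.3.2) all reduce the risk. That limits the likely harm. None of these measures tells the user which mode to program.

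**Conclusion.** The point holds as a drafting error in a safety instruction and should be fixed. Under 5.1 as written, a pacing-dependent subject has 0 of 2 permitted modes, and no other part of the protocol excludes that subject or supplies a different rule. That the sentence is inverted, or at least wrong, is a well-supported inference held with medium confidence; the exact wording intended depends on the Guide.

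A reader might infer that dependent subjects will be left unpaced in the scanner. The documents do not support that: the wording is advisory, physicians retain judgement, monitoring is continuous, and the number of such subjects may be zero. No endpoint, sample size or analysis is affected.

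**What to change.** Check the sentence against the MRI Technical Guide. Subject to that check, replace it with wording to this effect: asynchronous pacing should be used only if the subject is pacing-dependent, or is judged unable to go without pacing while the generator is in MRI Protection Mode, including subjects at risk of transient dependence, and after the risk of inducing arrhythmia has been weighed. Leave the condition on Off unchanged. Every subject then has a permitted mode.

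The cost is a one-sentence amendment. Because it concerns subject safety, section 15 requires Ethics Committee approval before it takes effect; sites should then be notified. Eligibility criteria, sample size and analyses stay as they are.

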***NOTE: In MRI Protection Mode there is no antitachycardia therapy available.***

Refer to the *BSC ImageReady MR Conditional Defibrillation System MRI Technical Guide*, here referred to as the *BSC MRI Technical Guide*, for additional information

regarding MRI Protection Mode.

### **5.2. MRI Protection Mode Time-out Function**

The MRI Protection Mode Time-out function allows the user to choose the length of time the PG remains in the MRI Protection Mode before returning to previous settings. MRI Protection Mode is programmed using the PRM. The Time-out feature has programmable values of OFF, 3, 6, 9 and 12 hours. At the conclusion of the programmed duration the PG returns to the previously programmed therapy parameters and settings. MRI Protection Mode may also be exited manually at any time during the time-out period. If the MRI Protection Time-out value is programmed to OFF, the patient will not receive Bradycardia pacing, Cardiac Resynchronization Therapy, or Tachycardia therapy until the PG is programmed out of MRI Protection Mode and back to previous operation. Refer to the BSC MRI Technical Guide for additional information on the MRI Protection Mode Time-out Function.

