#### **12.7.3.1. Programming MRI Protection Mode**

Prior to undergoing an MR scan, the ImageReady System must be programmed to the MRI Protection Mode and an appropriate pacing mode is set using the PRM. The PRM is to be kept ON and in MRI Zone I or II as close to the MRI room as possible.

WARNING: The PRM is MR Unsafe and must remain outside the MRI site Zone III (and higher) as defined by the American College of Radiology Guidance Document for Safe MR Practices. Under no circumstances should the PRM be brought into the MRI scanner room, (Zone IV), or the control room (Zone III). Programming the PG to MRI Protection Mode

should be done as close to the planned start of the MR scan as possible.

1. Start monitoring the subject
2. Program the MRI Protection Time-out (nominal setting: 6 hours; programmable values are OFF, 3, 6, 9, 12 hours)
3. Program the PG to the MRI Protection Mode, set up appropriate pacing parameters
4. Print the MRI Protection Settings Report. This report documents the MRI Protection Mode settings and details.
  - a. If the Time-out feature is used, the report includes the exact time and date when MRI Protection Mode will expire. If the Time-out feature is used, the MRI technologist/radiologist must verify that adequate time remains to complete the scan and to exit the MR scanner room.

Please refer to the *BSC MRI Technical Guide* for more information regarding PG MRI Protection Mode programming and other associated MRI warnings, cautions, and potential adverse events.

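### Protocol Sections 5.1 and 5.2 contradict each other on bradycardia pacing when an asynchronous MRI Protection mode is combined with Time-out OFF

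*Combined protocol and SAP*

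**What the plan says.** Three places in the protocol describe pacing while the pulse generator is in MRI Protection Mode.

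- **Section 5.1 (MRI Protection Mode)** offers asynchronous pacing (DOO, AOO, VOO) or no pacing. It ties the absence of therapy to one setting: "If MRI Protection Brady Mode is programmed to Off, the subject will not receive therapy until MRI Protection Mode is exited". Its list of suspended functions includes bradycardia sensing and tachycardia detection and therapy, but not bradycardia pacing.
- **Section 5.2 (MRI Protection Mode Time-out Function)** describes the Time-out as a duration setting that "allows the user to choose the length of time the PG remains in the MRI Protection Mode before returning to previous settings". For a Time-out set to OFF it then states that "the patient will not receive Bradycardia pacing, Cardiac Resynchronization Therapy, or Tachycardia therapy until the PG is programmed out of MRI Protection Mode". Brady Mode is not mentioned.
- **Section 12.7.3.1 (Programming MRI Protection Mode)** gives the steps at the MRI Visit. Step 2 sets the Time-out, with "nominal setting: 6 hours; programmable values are OFF, 3, 6, 9, 12 hours". Step 3 is separate: "Program the PG to the MRI Protection Mode, set up appropriate pacing parameters".

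The SAP does not address either setting.

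**The concern.** Two different settings can be OFF, the Brady Mode and the Time-out, and the protocol attaches loss of bradycardia pacing to each of them in different sections. A site that selects an asynchronous mode and leaves the Time-out OFF finds in 5.1 that the subject is paced and in 5.2 that the subject is not.

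What is at stake is whether staff correctly expect pacing during the scan. An error is possible in either direction. Someone relying on 5.1 may count on pacing that, if 5.2 is literally true, is absent. Someone relying on 5.2 may not expect pacing that, if 5.1 is true, is being delivered; Section 20.3 lists competition between fixed-rate pacing and the intrinsic rhythm among the scan risks.

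Section 5.1 also attaches a clinical judgement to the no-pacing state, that the subject can do without pacing. If 5.2 is literally true, Time-out OFF produces the same state, yet neither 5.2 nor 12.7.3.1 attaches that judgement to it. Exclusion criterion 4 and cardiology Condition of Use 5 concern only the absence of tachycardia protection.

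**Working it through.** No arithmetic underlies the contradiction, so the check is to read the sections side by side for each pairing of the two settings.

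| Brady Mode | Time-out | Section 5.1 | Section 5.2 | Conflict? |
|---|---|---|---|---|
| Off | OFF | no pacing | no bradycardia pacing | no |
| Off | 3, 6, 9 or 12 h | no pacing until the mode is exited | previous settings return when the time expires | no |
| DOO, AOO or VOO | 3, 6, 9 or 12 h | asynchronous pacing | does not deny pacing | no |
| DOO, AOO or VOO | OFF | asynchronous pacing | no bradycardia pacing | **yes** |

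**Is the fourth row permitted?** Yes. Section 12.7.3.1 lists OFF among the Time-out values and sets pacing in a later step, with no rule linking the two. Section 12.12 applies the same flow to medically necessary scans, so the combination can arise there too.

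**How much of the setting space is affected?** Taking the values as listed, there are 4 Brady Mode options (DOO, AOO, VOO, Off) and 5 Time-out values, so 4 × 5 = 20 pairings. The conflict covers 3 × 1 = 3 of them. This counts settings, not frequency of use; the documents give no figure for how often sites would choose either setting.

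**Which therapies are affected?** Bradycardia pacing only. On tachycardia therapy the sections agree: it is unavailable in the mode under both. Section 5.1 does not mention cardiac resynchronization, so there is nothing to set against 5.2 on that point.

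**Does another document settle it?** Not from what is available. Sections 5.1, 5.2 and 12.7.3.1 all refer to the Technical Guide for more information, but Section 6 says that where the two differ the protocol extends the Guide. A site therefore cannot assume that the Guide overrides the sentence in 5.2.

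**Possible origin, as inference only.** The revision history records that pacing in MRI Protection Mode was added at revision AC and lists the sections changed; 5.2 is not among them. The conflict stands in the current text whether or not that is the cause.

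**The case against.** The best reply is that 5.2 is loosely worded, not wrong. The section is about duration, and the disputed sentence ends by referring to a return to previous operation. On that reading it warns only that with Time-out OFF nothing restores the subject's usual therapy automatically, and bradycardia pacing there means the usual pre-scan pacing. This is plausible, but it is not written. The sentence lists bradycardia pacing beside tachycardia therapy, which is wholly absent in the mode, so a reader has reason to take both in the same way.

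A second reply is that the operating steps in 12.7.3.1 treat pacing as a separate choice, consistent with 5.1. That is so, but those steps do not say what Time-out OFF does, and a reader looking that up is led to 5.2.

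Several replies do limit the point:

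- **Subjects who need pacing.** A reader might infer a particular hazard for them. Section 5.1 says asynchronous pacing is for pacing-independent subjects only, so as written the conflicting combination should not arise in a subject who depends on pacing.
- **Safeguards.** Section 12.7.3.2 requires continuous ECG monitoring by an investigator, active alarms, voice and visual contact, and an external defibrillator with trained staff. Section 12.7.3.1 keeps the programmer on and near the MRI room.
- **Records.** The MRI Protection Settings Report documents the mode settings, and Table 12-6 requires it to be retained at the center. A new eCRF field is not needed.

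**Conclusion.** The contradiction is real as the text stands, and it is narrow. It exists for an asynchronous Brady Mode with Time-out OFF and nowhere else; the nominal Time-out is 6 hours. It is an internal inconsistency, wrong as written, not a design choice. It should be corrected because it concerns what sites are told about device behavior during the scan.

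Two stronger readings are tempting and are not supported:

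- **A general conflict about pacing during the scan, touching every scanned subject** (at least 8 + 8 = 16, with 20 planned). There is no conflict at any timed setting or with Brady Mode Off, and the documents do not say how many subjects would have the conflicting settings.
- **An effect on the primary safety endpoint.** Sections 13.1.1 and 23.2 define an event as a complication (a serious adverse event or permanent loss of device function) related to the MR scan and the ImageReady System, with the relation to the scan adjudicated by an external committee. Neither setting enters that definition, and the settings actually programmed are on record. No effect on any endpoint, the sample size or the analysis is shown.

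The conclusion rests on reading 5.2 as written and on the Technical Guide not having been available. It takes no position on which account of pacing is right.

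**What to change.** Reconcile Sections 5.1, 5.2 and 12.7.3.1 with each other and with the Technical Guide. State separately what Time-out OFF does and what Brady Mode Off does, including whether asynchronous pacing is delivered when the Time-out is OFF. Because Section 12.12 relies on the same flow, the corrected wording should cover medically necessary scans as well. Notify the sites.

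The cost is a protocol wording change and a short site notice. No new data collection is needed, and the SAP does not change.
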